466 regions. Participating paramedics will be trained in this algorithm before recruitment commences, with a refresher at
467 the mid-point of patient enrolment. The use of such an algorithm reflects routine practice, in that paramedics will
468 usually follow a specified protocol or “airway ladder” when managing the airway during OHCA. This approach will
469 standardise care in each trial arm, and all other elements of the care pathway will be identical.
470

471 Care will proceed as normal for OHCA patients enrolled in the trial, aside from the initial airway management. All
472 other interventions will proceed according to standard resuscitation guidelines that are disseminated widely in the
473 United Kingdom and internationally.
474

475 Patients who die at the scene will be managed in accordance with nationally disseminated ambulance service protocols
476 (e.g. recognition of life extinct, or confirmation of death). The remaining survivors will be transported to hospital, with
477 approximately half of these admitted to an intensive care unit (ICU). These patients will be treated using standard post-
478 OHCA care pathways.
479

480 **4.6 Primary and secondary outcomes**

481

482 **4.6.1 Primary outcome**

483

484 The primary outcome will be the modified Rankin scale (mRS) score measured at hospital discharge. However if the
485 patient remains in hospital for more than 30 days after the OHCA, the primary outcome (mRS) will be assessed at the
486 30 day time point instead of at discharge. The mRS which incorporates survival to discharge is widely used in OHCA
487 research[28, 29]. mRS is usually presented dichotomously as good recovery (0-3) or poor recovery/death (4-6).

488

489 All enrolled patients are eligible. We will collect survival data and mRS at hospital discharge with the prior
490 permission of the Health Research Authority Confidentiality Advisory Group (CAG), thereby ensuring close to 100%
491 data ascertainment.

492

493 For patients that survive to hospital discharge (or are still inpatients 30 days after their OHCA) the mRS will be
494 determined by a research nurse who will assess the patient using a simple flow chart that has been previously used to
495 assess patients who have had a cardiac arrest[30]. Any patient who does not survive to discharge will automatically be
496 assigned a score of six (dead) .

497

498 **4.6.2 Secondary outcomes**

499

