840 has since been acquired by South Western Ambulance Service, which has a pool of >1,500 eligible paramedics. The
841 three other ambulance services that have committed to the research have a combined pool of >3,200 paramedics.
842 Therefore, the four centres have eight times the paramedics of the feasibility study.

843

844 Based on our feasibility work we are confident we can enrol 1,200 OHCA patients per year in each of four
845 participating ambulance trusts, giving >9,000 patients over two years of recruitment.

846

847 **5.9 Participant recruitment**

848

849 **5.9.1 Paramedics**

850

851 Paramedics in the 4 trusts who have provided formal letters of support for the study will be invited to participate in the
852 study through a process of informed consent (Section 9.5). The study will be well publicised in participating
853 ambulance trusts using routine communications and bulletins, supplemented by personal invitation letters, posters and
854 awareness-raising events.

855

856 **5.9.2 Patients**

857

858 For this study we are using a model of deferred consent for survivors. All eligible patients attended by a participating
859 paramedic will be automatically enrolled in the study. For details on how these patients are identified see section 5.6.1.

860

861 **5.10 Discontinuation/withdrawal of participants**

862

863 If a participant wishes to withdraw from the study after providing consent, we will continue to analyse any data already
864 collected but no further data collection will take place.

865

866 **5.11 Frequency and duration of follow up**

867

868 Follow-up will occur at 3 and 6 months (\pm 4 weeks) after OHCA. The follow up will usually be carried out by
869 telephone or as a postal or online questionnaire co-ordinated by the Bristol CTEU. If this proves to be impractical,
870 follow up may be carried out by the research nurse and may occur in hospital, but more commonly at an outpatient
871 appointment (ideally coinciding with routine clinical follow-up) or in the patient's home/usual place of residence. The
872 primary and secondary outcome measures have been selected to be versatile in this regard, and have been validated for
873 telephone administration [41-45].

874

875 **5.12 Likely rate of loss to follow-up**

876

877 In the feasibility study 7% of paramedics withdrew from the study during the 12 month data collection phase and 86 %

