878 of patients discharged from hospital consented to follow up at 3 months. We would expect similar figures for this
879 study.

880

881 **5.13 Expenses**

882

883 A payment of overtime and travel expenses will be made to paramedics each time they attend one of the study training
884 sessions. The initial training session is mandatory for all paramedics who wish to take part in the study and attendance
885 at the refresher training and exit training will be strongly encouraged.

886

887 No expenses will be payable to participants because participants will not be required to make any additional visit to
888 hospital, to their GP or to any other health or welfare professional for the study.

889

890

891 **6. STATISTICAL ANALYSES**

892

893 **6.1 Plan of analysis**

894

895 The primary outcome of mRS at discharge or 30 days post OHCA (presented dichotomously as good recovery (0-3) or
896 poor recovery/death (4-6)), and other binary outcomes, will be analysed using a multilevel logistic regression model, in
897 which the data are nested within attending paramedic. Repeated mRS scores will be analysed using multilevel logistic
898 regression for repeated measures. Survival to 6 months and other time-to-event outcomes will be analysed using

AIRWAYS-2

21st December 2017

Protocol – version 6.0.

899 survival analysis methods, again allowing for clustering of patients by paramedic. Patient responses to the individual
900 EQ-5D questions will simply be described because these will be available only for survivors. Overall quality of life
901 utility scores and patient survival will be analysed jointly to assess whether the use of the i-gel supraglottic airway
902 device simultaneously improves the patient's quality of life and reduces the risk of death.

903

904 Enrolled patients who are subsequently identified as being ineligible will remain within the trial and be included in
905 analyses with the exception of a) patients who were subsequently found to have been previously enrolled in the trial; b)
906 patients who were inadvertently enrolled in the study due to being treated as a study participant by a paramedic who
907 arrives later than second at the patient's side; c) patients who are subsequently identified as being children (aged < 16
908 years); individuals aged 16 and 17 years will be included in analyses." . Analyses will be done according to the
909 principle of intention-to-treat, and reported according to the CONSORT guidelines [46, 47].

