1873 quartile range (IQR) if the distribution is skewed), and categorical data will be summarised as a number and
1874 percentage. The summary statistic headings given in **Tables T4** and **T5** are those we expect to use based on a-
1875 priori knowledge of the clinical measurements gained from previous studies. However, if distributional
1876 assumptions are not satisfied, changes will be made.

1877 Statistical tests to compare data not listed as outcomes will not be performed. Secondary outcomes 4
1878 (sequence of airway interventions delivered) and 7 (airway management in place when ROSC was achieved
1879 or resuscitation discontinued) will be described but not formally compared.

1880 **6.2 Primary and secondary outcome data**

1881 **6.2.1 Adjustment in models**

1882 The intention is to adjust the models for the three stratification (design) factors: ambulance trust (four levels),
1883 clinical experience (two levels) and the location of the paramedic’s base ambulance station (two levels) as
1884 fixed effects, and paramedic as a random effect (or a shared frailty term in the time to event model). For the
1885 mRS model where the majority of patients will have a poor outcome/death, the data may be insufficient to
1886 allow estimation of regression coefficients for all these variables. If this is the case, inestimable stratification
1887 variables will be dropped from the model and will be noted in a footnote. For the time to death model, if a cox
1888 model is used the analysis will be stratified by trust (to allow for varying baseline hazards) and adjusted for
1889 the other design factors. If either of the design factors do not meet the proportional hazards assumptions,
1890 stratification by these factors will also be implemented.

1891 **6.2.2 Data presentation and analysis models**

1892 For intention to treat analyses, data will be presented and analysed by the allocated group of the first A2
1893 paramedic on scene, regardless of what airway management the patient received. For per-protocol analyses
1894 (see sections 6.2.5 and 6.2.6), data will be presented and analysed by the allocation of the first advanced
1895 airway management used; if neither i-gel nor intubation was used (or if another SGA was used before an i-gel
1896 or intubation), the patients will be excluded from per-protocol analyses.

1897 All analyses and data presentation will be by intention to treat unless otherwise stated in the Table heading.

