- 1972 There will be no missing data for any of the randomisation factors (by design).
- 1973 Missing outcomes:
- 1974
 - If the proportion of missing data is less than 5% then complete case analysis will be performed (i.e.
1975 excluding cases with missing data).
 - If the proportion of missing data is above 5% multiple imputation methods will be considered. A general
1976 imputation model that uses an iterative procedure to generate imputed values will be used to generate
1977 multiple complete data sets (e.g. using Stata’s mi impute). The model of interest will be the fitted to each
1978 of the complete data sets and effect estimates combined using Rubin’s rules.
- 1979
- 1980 If appropriate (the level of missingness is >20%) then any variables that are predictive of missingness will be
1981 identified, and if there is reason to suggest that an assumption of missing at random (MAR) given these
1982 variables is reasonable then such variables will be adjusted for in the models of interest. These models can be
1983 shown to provide unbiased estimates of the treatment effect and moreover multiple imputation approaches
1984 would not be expected to recover any additional information.
- 1985 **6.2.8 Multiple testing**
- 1986 No formal adjustment will be made for multiple testing. However as previously described formal statistical
1987 comparisons will not be made for outcomes with low event rates and only pre-specified subgroup analyses

1988 will be performed. Consideration will be taken in interpretation of results to reflect the number of statistical
1989 tests performed and the consistency, magnitude and direction of treatment estimates for different outcomes.

1990 **6.3 Safety data**

1991 Safety data are only collected for events which are unexpected and potentially related to the intervention. All
1992 such events will be detailed along with descriptions of patients' airway management pathway. **Table T9**
1993 summarises such events, as captured via serious adverse event (SAE) report forms and full details will also be
1994 given as listings (see **Table T10**).

1995 No formal comparisons between groups will be made as numbers of events are expected to be small.

1996

1997 **7. AMENDMENTS TO THE SAP**

Previous version	Previous date	New version	New date	Brief summary of changes

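### Above 20% missing, SAP 6.2.7 allows adjustment for predictors of missingness that treatment may itself affect, and wrongly presents this as unbiased in general

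*Protocol*

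**What the plan says.** SAP section 6.2.7 handles missing outcomes in three bands. Below 5%, complete cases are analysed. Above that, "If the proportion of missing data is above 5% multiple imputation methods will be considered", and the unchanged model of interest is fitted to each completed data set and combined by Rubin's rules. The third band reads "If appropriate (the level of missingness is >20%) then any variables that are predictive of missingness will be" identified; if MAR given these "variables is reasonable then such variables will be adjusted for in the models of interest". The section closes by saying that such models can be "shown to provide unbiased estimates of the treatment effect and moreover multiple imputation approaches" should not recover anything further.

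No candidate variables are named, and nothing restricts them to variables that precede treatment. Elsewhere (SAP 6.2.1) the models adjust only for the three stratification factors, with paramedic as a random effect or shared frailty.

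**The concern.** The third band treats two different questions as one. Whether data are MAR given a variable concerns the missingness mechanism. Whether the variable belongs in the treatment model depends on whether treatment can change it. If airway strategy affects a variable and that variable also predicts later outcome, conditioning on it removes the part of the effect that runs through it. It can also introduce bias from unmeasured causes shared by the variable and the outcome. MAR may hold exactly and the estimate still be wrong.

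Because paramedics are randomised, every patient variable is recorded after randomisation in calendar time. The boundary that matters is therefore the start of airway management. Age, sex, presenting rhythm, witnessed status and bystander CPR fall before it; length of ICU and hospital stay, both derived in SAP 5.4, fall after it. The rule does not distinguish between the two kinds.

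At stake is a pre-specified rule that operates where missingness is heaviest and could turn an estimate of the total effect into something else, while the plan describes it as unbiased.

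**Working it through.** The plan gives no figure for this rule, and its sample size does not bear on it. The check has two parts.

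**1. Are the two general statements true?** A large-sample simulation was run with 1,000,000 patients and a linear model. All parameters are assumed; none come from the documents. T is treatment (0/1), B a variable fixed before treatment, M a variable measured after it, and U an unmeasured cause of both M and outcome:

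- M = a·T + u·U + error
- Y = 0.5·T + 0.6·M + 0.5·B + u·U + error
- total effect of T = 0.5 + 0.6·a, which is 0.80 for a = 0.5 and 0.50 for a = 0
- logit P(missing) = −1.2 + 0.8·B, or −1.2 + 0.8·M

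Missingness depends only on B or only on M, so MAR holds given that variable.

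| Missingness driven by | a | u | % missing | True effect | Complete cases, unadjusted | Complete cases, adjusted for the driver | Imputed using M and B, model unchanged |
|---|---|---|---|---|---|---|---|
| B | 0.5 | 0.7 | 25.7 | 0.80 | 0.80 | 0.80 | 0.80 |
| M, affected by T | 0.5 | 0 | 29.4 | 0.80 | 0.77 | 0.50 | 0.80 |
| M, affected by T | 0.5 | 0.7 | 30.3 | 0.80 | 0.74 | 0.34 | 0.80 |
| M, not affected by T | 0 | 0.7 | 26.6 | 0.50 | 0.49 | 0.49 | 0.49 |

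The two biased results can be confirmed by algebra. With u = 0, adjusting for M leaves the direct effect, 0.5. With u = 0.7, the coefficient of T is 0.5 − 0.7 × [0.7/(0.7² + 1)] × 0.5 = 0.5 − 0.164 = 0.336.

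In these examples adjustment removes 0.30/0.80 = 37.5% or 0.46/0.80 = 57.5% of the effect. Unadjusted complete cases lose 0.03/0.80 = 3.75% or 0.06/0.80 = 7.5%. So where treatment affects the predictor, the prescribed adjustment is further from the truth than no adjustment, and imputation recovers what both lose. For B, and for an M that treatment does not affect, there is no material bias.

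**2. Where could the rule operate?**

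- *Primary outcome.* Protocol 4.6.1 collects survival and mRS with the prior "permission of the Health Research Authority Confidentiality Advisory Group (CAG), thereby ensuring close to 100" per cent ascertainment. The rule is unlikely to be reached.
- *3- and 6-month mRS and EQ-5D.* Protocol 5.12 reports that in the feasibility study 86% "of patients discharged from hospital consented to follow up at 3 months", so 14% did not. SAP 3.7 confines population 5 to survivors who agree to active follow-up and supply data at one time point or more. The 14% are outside that denominator.
- *EQ-5D with deaths scored zero (SAP 5.3), over all trial patients.* Survivors are about 9% of patients, so missingness cannot exceed about 9%, and non-consent contributes about 0.14 × 9% = 1.3%.
- *Chest compression fraction.* This is limited to two trusts and started partway through the trial (SAP 2.4, 3.7). No completeness figure is given.

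Only non-response within population 5, or incomplete compression recording, could plausibly take an outcome past 20%. The documents quantify neither.

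**The case against.** The strongest reply is that the rule is conditional. It applies where appropriate and where MAR is judged reasonable, and a sensible analyst might find only baseline predictors, for which the claim of unbiasedness holds in the linear case. That stands: the rule could bias the effect, and nothing in the SAP says that it will.

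Several stronger readings are tempting but unsupported:

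- *That discharge mRS or EQ-5D would be the offending covariate.* SAP 6.2.2 analyses discharge, 3- and 6-month values together as the response in mixed-effects models with patient random effects. The discharge value is already an outcome there, and under MAR the likelihood already uses it when later values are missing. Length of stay is the clearer example.
- *That 14% non-consent brings 20% within reach.* As shown, non-consenters are outside population 5. Protocol 4.3.4 and 6.1 also expect near-complete follow-up among those who consent.
- *That odds ratios would cease to be comparable across time points.* One longitudinal model has one covariate set for all of them.

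It is also fair that the simulation is a single-endpoint linear model with assumed parameters, not the SAP's repeated-measures logistic model, so its percentages are not forecasts for this trial. That does not rescue the SAP's sentence, which is general and is refuted by one counterexample in which MAR holds.

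**Conclusion.** The rule is wrong as a general statement and should be corrected, but the consequence is small. It permits adjustment for variables that treatment affects and asserts, without condition, that the result is unbiased and that imputation has nothing to add. Both assertions fail when the predictor is a consequence of airway strategy; in the assumed example 0.80 becomes 0.50 or 0.34. They hold in the linear case when the predictor is fixed before airway management and no useful auxiliary variables exist.

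The point is confined to secondary outcomes: 3- and 6-month mRS and EQ-5D, possibly chest compression fraction. It rests on two things that the documents do not settle: that missingness in one of these passes 20%, and that a predictor of it is affected by treatment. A reader might infer a threat to the primary result; the documents do not support that. SAP 6.2.2 also keeps outcomes 10 to 13 out of the primary paper, and population 5 is already restricted to consenting survivors, so this rule would not be the only limit on interpreting those comparisons.

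**What to change.** Amend SAP 6.2.7 in three places:

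1. Limit any covariate added to the analysis model because of missingness to variables fixed before airway management, such as age, sex, presenting rhythm, witnessed status and bystander CPR.
2. Use predictors of missingness measured later, such as length of ICU or hospital stay, only as auxiliary variables in the imputation model, and leave the treatment model unchanged.
3. Delete the closing sentence on unbiasedness and no gain from imputation, or restrict it to pre-intervention covariates with no auxiliary variables available.

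The cost is a short SAP amendment and a little more programming; the primary analysis is untouched. One drawback should be noted when reporting: in logistic models even added baseline covariates change the conditional odds ratio being estimated, so the covariate set should be stated beside any such estimate.

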APPENDIX A: SKELETON TABLES AND FIGURES

Section	Outputs
Section 1 Population	Tables, figures and listings detailing the study population Figure F1 Flow of participants Figure F2 Flow of patients Figure F3 Predicted and actual recruitment Figures F4 & F5 Predicted and actual recruitment by trust Table T1 Initial cardiac arrest details by enrolment status Table T2 Protocol deviations Table T3 Withdrawals
Section 2 Baseline and intervention data	Summary tables of demographic information Table T4 Patient demography and cardiac arrest details Table T5 Intervention and post-intervention details Figure F6 Interventions received by paramedic allocation
Section 3 Primary and secondary outcome data	Summary data and group estimates for primary and secondary outcomes Table T6 Primary outcome Table T7 Secondary outcomes Table T8 Longitudinal secondary outcomes Figure F7 Subgroup analyses
Section 4 Safety data	Summary tables and listings of all adverse events and serious adverse events Table T9 Unexpected serious adverse events Table T10 Details of unexpected serious adverse events

2003

2004
2005

Figure F1 Flow of paramedics and patients

[figure not shown]
note:

- ¹ XXX patients (XXX intubation, XXX i-Gel) received at least one airway management attempt but did not receive i-Gel or intubation. These patients received another SGA.
- ² of the XXX paramedics who withdrew after randomisation, XXX attended an OHCA (XXX Intubation, XXX i-gel) and XXX had not attended an OHCA (XXX intubation, XXX i-gel). Of the former, XXX attended one or more trial patients (XXX Intubation, XXX i-gel). The median number of OHCA attended per withdrawn paramedic is XXX for Intubation (IQR=XXX) and XXX for i-gel (IQR=XXX). The median number of trial patients attended per withdrawn paramedic is XXX for Intubation (IQR=XXX) and XXX for i-gel (IQR=XXX).
- ³ XXX patients in the intubation arm and XXX patients in the i-gel arm withdrew prior to 3 months follow-up.
- ⁴ XXX patients in the intubation arm and XXX patients in the i-gel arm withdrew after 3 months and prior to 6 months follow-up.

2006
2007
2008
2009
2010

[figure not shown]
Figure F2

Flow of patients

2011

Figure F3 Predicted and actual recruitment

[figure not shown]

2012
2013

2014 **Figure F4 Predicted and actual recruitment by trust (SWAST and YAS)**

2015
2016 **Figure F5 Predicted and actual recruitment by trust (EMAS and EAST)**

2017

2018

Table T1 Initial cardiac arrest details by enrolment status

	EXCLUDED FROM STUDY					
	Resuscitation attempted but not attended by A2		Resuscitation attempted and attended by A2		Resuscitation attempted, attended by A2, and eligible. I.e. trial patients	
	(n=)		(n=)		(n=)	
	n	%	n	%	n	%
Age (median, IQR)						
Male gender						
999 call to first crew arrival time (mins; median, IQR)						
Presenting rhythm						
Asystole						
VF						
Pulseless VT						
PEA						
Unknown						
Event witnessed						
By EMS						
By bystander						
Bystander CPR						

2019

Note: XXX patients were attended by an A2 paramedic but were not resuscitated.

2020 **Table T2 Protocol deviations**

	Randomised to intubation (n=XX)		Randomised to i-gel (n=XX)		Overall (n=XX)	
	n	%	n	%	n	%
All trial patients						
Wrong paramedic enrolled patient						
Resulted in randomised allocation crossover						
Enrolling paramedic did not perform any airway management but another paramedic did						
Trial patients with at least one advanced airway management attempt performed						
Enrolling paramedic did not perform allocated intervention on first advanced airway attempt						

Note. All patients grouped by the allocation of the first A2 paramedic on scene.

2021
2022
2023

2024 **Table T3 Withdrawals**

	Randomised to intubation (n=XX)		Randomised to i-gel (n=XX)		Overall (n=XX)	
	n	%	n	%	n	%
Any withdrawal (paramedics)						
Decision taken by						
Study team						
Paramedic						
Reason for withdrawal						
Reason 1						
Reason 2						
.....						
Any withdrawal (trial patients)						
Timing of withdrawal						
Pre-discharge						
Post-discharge						
Decision taken by						
Health care professional						
Patient						
Reason for withdrawal						
Reason 1						
Reason 2						
...						
...						

Note. This form only applied to patients who consent to active or passive follow-up

2025
2026

2027

Table T4 Patient demography and cardiac arrest details

	Randomised to intubation (n=XX)		Randomised to i-gel (n=XX)		Overall (n=XX)	
	n	%	n	%	n	%
DEMOGRAPHY						
Male gender						
Age (median, IQR)						
INITIAL CARDIAC ARREST DETAILS						
999 call to first crew arrival time (mins; median, IQR)						
First crew arrival to A2 arrival time (mins; median, IQR)						
999 call to A2 arrival time (mins; median, IQR)						
Presenting rhythm						
Asystole						
VF						
Pulseless VT						
PEA						
Arrest witnessed						
By EMS						
By bystander						
Bystander/responder CPR before response vehicle arrived						
Bystander/responder defibrillation before response vehicle arrived						
If yes, ROSC achieved						
ON ARRIVAL OF A2 PARAMEDIC						
Patient had ROSC on arrival						
Airway management in progress						
None						
BVM only						
OPA						
NPA						
I-gel						
Intubation						
Other SGA*						
Other*						
Successful ventilations ongoing						

* Details will be provided

2028

2029

2030

2031

Table T5 Intervention details (excluding secondary outcomes)

	Randomised to intubation (n=XX)		Randomised to i-gel (n=XX)		Overall (n=XX)	
	n	%	n	%	n	%
A2 AIRWAY MANAGEMENT DETAILS						
At least one airway management attempt reported by study paramedic						
Reasons for not reporting at least one airway management attempt						
Resuscitation successful/ceased						
Another paramedic managed airway						
Enrolling paramedic managed airway but cannot remember details						
Patient had a tracheostomy						
Other						
Patient received at least one advanced airway management attempt by an A2 paramedic						
Intubation						
I-gel						
Other SGA						
CO ₂ monitoring/ capnography used						
If no, reason:						
Unavailable						
Faulty equipment						
N/A- no advanced airway management						
If yes, type of CO ₂ monitoring						
Colour only						
Capnometry (number only)						
Capnography (waveform)						
Mechanical CPR used during resuscitation						
Airway management handed over during pre-clinical care						
If yes, to whom						
Doctor						
Nurse						
Paramedic						

[figure not shown]
2032

2033

2034

2035

Figure F6 Interventions Received By Paramedic Allocation

[1] XX additional patients received an alternative supraglottic airway device only. Of which XX (%) had a good mRS score, XX (%) had a bad mRS score, XX was missing mRS, and XX (%) had an mRS of 6.

[2] XX additional patients received an alternative supraglottic airway device only. Of which XX (%) had a good mRS score, XX (%) had a bad mRS score, XX was missing mRS, and XX (%) had an mRS of 6.

2068

Table T6 Primary outcome (mRS) and survival status

	Randomised to intubation (n=XX)		Randomised to i-gel (n=XX)		Estimate ¹ (95% CI)	p-value
	n	%	n	%		
mRS (0 to 3; good recovery)					OR ²	
0 (no symptoms)						
1						
2						
3						
4						
5						
6 (deceased)						
Time from OHCA to time mRS was assessed (median, IQR)						
Survival status:						
Died on scene						
Died prior to ICU admission						
Died prior to ICU discharge						
Died prior to hospital discharge						
Survived to hospital discharge						
Time to death (hours; median, IQR)					HR ³	
Time to death 0-72h (hours; median, IQR)					HR	
72 hour survival					OR	

2069 ¹OR=Odds ratio, HR=Hazard ratio

2070 ²ICC

2071 ³ ICC

2072

2073

2074

Table T7 Secondary outcomes and related post-intervention details

	Randomised to intubation (n=XX)		Randomised to i-gel (n=XX)		Estimate ¹ (95% CI)	p-value
	median	IQR	median	IQR		
Compression Fraction					MD/GMR	
	Randomised to intubation (n=XX)		Randomised to i-gel (n=XX)		Estimate ¹ (95% CI)	p-value
	n	%	n	%		
AIRWAY MANAGEMENT DETAILS						
Actual sequence of airway interventions delivered						
Sequence 1						
Sequence 2						
.....						
Initial ventilation success (first two attempts) of first advanced airway management						
Intubation						
I-gel						
Other SGA						
Total					OR	
Any ventilation success						
Intubation						
I-gel						
Other SGA						
Total					OR	
Any loss of previously established airway						
Intubation						
I-gel						
Other SGA						
Total					OR	
Regurgitation before initial i-gel/intubation attempt					OR	
If yes, aspiration					OR	
Regurgitation during or after initial i-gel/intubation attempt					OR	
If yes, aspiration					OR	
Any ROSC during advanced A2 airway management					OR	

[figure not shown]
Any ROSC during any A2 airway management						
Advanced airway management in place when patient first had ROSC						
Intubation						
I-gel						
Other SGA						
Other						
Airway management in place on final attempt by A2 paramedic in those who died on scene						
Intubation						
I-gel						
Other SGA						
Other						
Airway management in place when patient first had ROSC or on final attempt by A2 paramedic in those who died on scene						
Intubation						
I-gel						
Other SGA						
Other						
Total						
Airway management in place on final attempt by A2 paramedic in those who were admitted to ED						
Intubation						
I-gel						
Other SGA						
Other						
	Randomised to intubation (n=XX)		Randomised to i-gel (n=XX)		Estimate¹	
	n	%	n	%	(95% CI)	p-value
ED STAY						
Admitted to ED/ hospital						
ROSC on ED/hospital admission						
Survived to ED discharge						
ICU STAY						
Admitted to ICU from ED						
Survived to ICU discharge						
Duration of initial ICU stay in patients who survived to ICU discharge (hours; median, IQR)						

Duration of ICU stay in patients who died in ICU (hours; median, IQR)
Duration of ICU stay in all patients admitted to ICU from ED (hours; median, IQR)

HOSPITAL STAY

Survived to hospital discharge
Duration of hospital stay in patients who survived to discharge (days; median, IQR)
Duration of hospital stay in patients who died before discharge (hours; median, IQR)
Duration of hospital stay in all patients admitted to ED (hours; median, IQR)

2075
2076
2077
2078
2079

¹OR=Odds ratio (from logistic or, where marked *, multinomial regression), MD=mean difference, GMR=Geometric mean ratio

[figure not shown]
Table T8 Longitudinal secondary outcomes

	Randomised to intubation (n=XX)		Randomised to i-gel (n=XX)		Overall (n=XX)	
	n	%	n	%	N	%
mRS (0 to 3; good recovery)						
Discharge/30 days						
3 months						
6 months						
Treatment*time interaction						
Overall						OR
	Randomised to intubation (n=XX)		Randomised to i-gel (n=XX)		Overall (n=XX)	
	n	%	n	%	N	%
EQ5D index score (median, IQR)						
Discharge/30 days						
3 months						
6 months						
Treatment*time interaction						
Overall						OR, GMR
EQ5D visual analogue scale score (median, IQR)						
Discharge/30 days						
3 months						
6 months						

Treatment*time interaction	
Overall	OR, GMR

2080
2081
2082
2083
2084
2085
2086
2087

Figure F7 Subgroup analyses (example for one subgroup analysis: event witnessed by ambulance staff)

2088
2089

Table T9 Unexpected serious adverse events

		Received Intubation first (n=XX)		Received i-gel first (n=XX)	
		n	%	n	%
Number of patients experiencing one or more SAEs					
Number of events					
Brief description of events					
Timing of events	Pre-surgery Post-surgery but pre-discharge Post-discharge				
Maximum intensity	Mild Moderate Severe				
Reason event classified as SAE	Resulted in death Is/was life threatening Resulted in persistent or significant disability/incapacity Prolonged ongoing hospitalisation/ caused hospitalisation Other				
Relatedness to intervention	Possibly related Probably related Definitely related				

2090
2091
2092
2093

Table T10 Details of unexpected serious adverse events

Study ID=	Intervention randomised to=	Interventions received=	Patient withdrawn from study (and when)=
OHCA date=	Hospital discharge date (if applicable)=	Death date (if applicable)=	Timing of SAE= Post-intervention but pre-discharge/ Post-discharge
Brief description of event=	Location=	Maximum intensity=	Relatedness=
SAE start date/time=	SAE resolution date/time=	Event resulted in death=	Event was life threatening=
Event resulted in persistent/significant disability/incapacity=	Event prolonged ongoing hospitalisation/resulted in hospitalisation=	Other reason for reporting as SAE (with details)=	
Initial report: full details	Initial report: action=	Initial report: other info=	
FUP 1: full details	FUP 1: action=	FUP 1: other info=	
FUP 2: full details	FUP 2: action=	FUP 2: other info=	

2094
2095
2096

2097
2098

